8 SAFETY

The Investigator and the Sponsor are responsible for monitoring the safety of patients who have entered the study. To capture the most potentially relevant safety information during a clinical trial, it is important that Investigators record accurate AE terms on the eCRF.

8.1 Adverse Event Definitions

8.1.1 Adverse Event

An AE includes any noxious, pathological, or unintended change in anatomical, physiological, or metabolic functions as indicated by physical signs, symptoms, and/or laboratory changes occurring in any phase of the clinical study whether or not temporally associated with the administration of study medication and whether or not considered related to the study medication. This definition includes an exacerbation of pre-existing medical conditions or events, intercurrent illnesses, hypersensitivity reactions, drug interactions, or clinically significant laboratory findings.

An AE does not include the following:

- Medical or surgical procedures, e.g., tooth extraction, transfusion, surgery (The medical condition that leads to the procedure is to be recorded as an AE.)
- Pre-existing conditions or procedures present or detected at the start of the study that do not worsen
- Hospitalization for elective surgeries or for other situations in which an untoward medical event has not occurred
- Abnormal laboratory value, unless it is clinically significant according to the Investigator, requires intervention, or results in a delay, discontinuation or change in the dose of study drug
- Overdose of study drug or concomitant medication unaccompanied by signs/symptoms; if sign/symptoms occur, the final diagnosis should be recorded as an AE.
- Pregnancy by itself, unless a complication occurs during pregnancy leading to hospitalization; in this case, the medical condition that leads to the hospitalization is to be recorded as the AE.
- A significant worsening of the disease under investigation including death which is captured as an efficacy parameter in this study and, thus, is not recorded as an AE.

8.1.2 Serious Adverse Event

A serious adverse event (SAE) is defined as an adverse event that results in any of the following outcomes:

- Death
- Life-threatening adverse experience (i.e., immediate risk of death from the event as it occurred; this does not include an adverse event that, had it occurred in a more serious form, might have caused death)
- Persistent or significant disability/incapacitation
- Inpatient hospitalization or prolongation of existing hospitalization

- Congenital anomaly/birth defect

Important medical events that may not result in death, be life-threatening, or require hospitalization may be considered serious when, based on medical judgment, they may jeopardize the patient or may require medical or surgical intervention to prevent one of the outcomes listed in this definition.

Hospitalizations due to the underlying disease will not be reported as an SAE unless there is reason to suspect a causal relationship with the study drug.

8.1.3 Unexpected Adverse Event

An AE or suspected adverse reaction is considered "unexpected" if it is not listed in the ALRN-6924 Investigator's Brochure or is not listed at the specificity or severity that has been observed; or, is not consistent with the risk information described in the protocol or elsewhere. For example, under this definition, hepatic necrosis would be unexpected (by virtue of greater severity) if the Investigator's Brochure referred only to elevated hepatic enzymes or hepatitis. Similarly, cerebral thromboembolism and cerebral vasculitis would be unexpected (by virtue of greater specificity) if the Investigator's Brochure listed only cerebral vascular accidents.

"Unexpected," as used in this definition, also refers to AEs or suspected adverse reactions that are mentioned in the Investigator's Brochure as occurring with a class of drugs or as anticipated from the pharmacological properties of ALRN-6924 but are not specifically mentioned as occurring with ALRN-6924.

8.2 Adverse Event Reporting Period

The AE reporting period begins from the date of the first study drug administration and ends 30 days after the last dose of study drug or a subsequent anticancer therapy is started, whichever occurs first. See [Section 8.4](#) for information about reporting SAEs. Information regarding the follow up of AEs can be found in [Section 8.5](#).

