Clinical activity or response will be evaluated by standard imaging assessments, such as computed tomography (CT), magnetic resonance imaging (MRI), and bone scans. In addition, [¹⁸F]-fluorodeoxyglucose positron emission tomography (FDG-PET) or other techniques considered clinically appropriate for the patient's specific disease type can be used. Anti-tumor activity will be assessed using RECIST 1.1 ([Appendix K](#)) for patients with solid tumors or using IWG (2014) criteria ([Appendix L](#)) for patients with lymphomas. The same imaging technique should be used at each assessment for a patient.

Positron Emission Tomography (PET) Scans:

- For patients with an FDG-avid lymphoma, FDG-PET imaging will be performed at baseline and post-baseline as outlined in IWG 2014 during DEP and in the EXP.
- For solid tumor patients, FDG-PET imaging may be performed at baseline and subsequently post-dose at the first occurrence of stable disease in applicable patients as an adjunct to determine anti-tumor activity, as outlined in RECIST 1.1. (Applicable patients are those who had an evaluable FDG-PET-scan performed prior to starting treatment with study drug.)

NOTE: PET/CT scans may substitute for contrast-enhanced CT scans provided the CT performed as part of a PET-CT is of similar diagnostic quality as a diagnostic CT with IV and oral contrast. As with CT-imaging, the same imaging technique should be used for each patient's PET assessment.

Phase 2a – Dose Expansion

Biopsies:

In the Phase 2a EXP PTCL cohorts, optional biopsies will be taken for PD and p53 status determination purposes: one during screening, one during treatment, and one or more at times of suspected and/or confirmed progression. In the palbociclib combination cohort, if a biopsy is taken for any reason during the study, the samples may be used for further analysis. Samples might be submitted for whole exome sequencing (with a paired germline sample) and RNA sequencing (RNAseq), and results will be compared between pre-treatment and on-treatment, and time of suspected and/or confirmed progression tumor samples for markers of disease response and resistance. Protein expression via immunohistochemistry and RNA expression via quantitative RT-PCR will be examined on specimens obtained prior to beginning treatment, during treatment with ALRN-6924, and then upon suspected and/or confirmed progression. Biopsy details may be found in the Laboratory Manual.

Clinical Activity:

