8.4 Adverse Event Reporting

Each AE is to be reported by the Investigator as serious or non-serious according to the definitions above. This classification that determines the regulatory reporting procedures to be followed is described in Table 5.

Table 5: Reporting Guidelines for Adverse Events

Gravity of AE	Reporting Time to Sponsor	Type of Report
Serious	Within 24 hours after the site becomes aware of the event	Initial SAE Report
	Within 4 working days after the site becomes aware of the event	Completed SAE Report
Non-Serious	Per AE eCRF page	Completed AE eCRF page

Any SAE, regardless of relationship to study treatment that occurs during therapy or within 30 days after the last dose of study treatment must be reported to the Sponsor within 24 hours after the site becomes aware of the event. The Investigator is encouraged to discuss with the study Medical Monitor any adverse experiences for which the issue of reportability is unclear or questioned. The initial report should be followed by submission of a more detailed SAE Report within 4 working days of the site's knowledge of the event.

If the SAE occurs more than 30 days following administration of the last dose of study treatment, SAEs should be reported only if considered related to study treatment. In the event of patient death, the reason for death should be recorded as the SAE, with 'death' recorded as the outcome on the SAE eCRF module.

The SAE also will be recorded as an AE on the AE eCRF page. Note: the SAE Report is different from the AE eCRF page. In areas of both forms where the same data are reported, the forms will be completed in a consistent manner. For example, the same term should be used for the AE on both forms, with the same start and stop dates, action taken, outcome, etc.

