8.5 Adverse Event and Serious Adverse Event Follow-Up

All AEs and SAEs observed while a patient is receiving study treatment should be followed until resolution, return to baseline, or it is deemed that further recovery is unlikely. For patients who have discontinued study treatment, all AEs and SAEs that occur within 30 days after the last administration of study treatment or withdrawal from the study must be reported unless the patient starts new anticancer therapy. Any AE or SAE deemed related to study drug should be followed until resolution or stabilization, or until the patient starts new therapy. All measures required for AE management and the ultimate outcome of the AE will be recorded in the source document and eCRF.

For SAEs occurring from the patient's first administration of study treatment, during the study or within 30 days of the last administration of study drug, the Investigator should submit follow-up reports to the Sponsor regarding the status of the SAE and the patient's subsequent course. Follow-up reports should be submitted until the SAE has subsided, until the condition stabilizes (in the case of persistent impairment), the patient receives alternative therapy, or the patient dies.

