⁷ PD (MIC-1 and CTC): Within 1 hour before the start of infusion (SOI), and 4 (±10 min) and 8 hours (±2 hours) after EOI.

PK: Within 1 hour before SOI; at EOI (+5 min) and at 30 min (±5 min), 1 hour (±5 min), 2 (±10 min), 4 (±10 min) and 8 hours (±2 hours) after EOI.

Immunogenicity: Within 1 hour before the SOI on Day 1.

Patients who are already enrolled in the expansion and consent to this PD/PK testing will have blood drawn at their next available cycle (i.e. if the next available cycle is Cycle 4, they will follow the PK/PD Cycle 1 testing at Cycle 4, and will follow the indicated Cycle 2 testing at Cycle 5).

⁸ PD (CTC and MIC-1) and PK: blood should be collected 24 hours (± 4 h) after the initiation of Day 1 infusion.

⁹ DEP only: PD (MIC-1 only) and PK: blood should be collected 48 hours (± 4 h) after the initiation of Day 1 infusion.

¹⁰In patients consenting to optional biopsies, buccal swab for germline DNA (EXP only)

¹¹ RECIST 1.1- (for solid tumor patients) or IWG 2014- (for lymphoma patients) compliant imaging for disease assessment and tumor measurements as well as laboratory-based assays (e.g., prostate specific antigen) for patients with relevant disease indications.

¹² During the first two cycles, ALRN-6924 should be administered in the morning to allow observation of delayed infusion reactions. In dosing regimen DR-A, ALRN-6924 will be infused over 1 hour (± 15 min). In dosing regimen DR-A-2, ALRN-6924 will be infused over 2 hours (± 15 min), with dexamethasone (4 mg orally or IV) administered 4 hours after the end of infusion to mitigate potential infusion reactions. At the end of the infusion for both DR-A and DR-A-2, IV fluids (saline) or oral fluids (500mL – 1000 mL) should be administered unless clinically contraindicated.

¹³ All concomitant medications taken within 28 days of beginning the study (Cycle 1 Day 1) until 30 days after last infusion or start of subsequent therapy must be reported in the relevant eCRF pages, including supportive care drugs and drugs used for treatment of AEs or chronic diseases.

¹⁴ AE reporting begins at the point of the first ALRN-6924 infusion until 30 days after last infusion or start of subsequent therapy; until all drug-related toxicities and ongoing SAEs have resolved, whichever is later; or until the Investigator assesses AEs as "chronic" or "stable."

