ECOG Performance Status	Within 7 days prior to Day 1	X			X		X						
Tumor Assessment/Imaging	Within 28 days prior to Day 1												
ALRN-6924 dosing ⁶		X			X		X						
Palbociclib dosing ⁶		Administered orally on Days 1 to 21 of each 28-day cycle with food											
Patient diary ⁷		Record daily during palbociclib dosing											

	Screening -21 days	Day 1	Day 2	Day 8 ± 1 d	Day 15 ± 1 d	Day 22 ±1 d	
Concomitant medications	Within 28 days prior to C1D1 until 30 days after last infusion or start of subsequent therapy						
AE assessment		AE collection period begins with first dose of ALRN-6924 until 30 days post last dose or start of subsequent therapy					

¹ HPV status must be determined only for tumors that are associated with HPV infection, including (but not limited to) cervical cancers, oropharyngeal cancer, head and neck squamous cell cancers or anal cancer, unless HPV status of the tumor is already known and documented.

² Blood pressure, pulse, respiration rate, body temperature.

Cycle 1, Days 1, 8, 15: On the days of drug administration vital signs will be recorded pre-dose (within 30 minutes prior to SOI) and at the following timepoints:

During infusion: 15 min (± 3 min) and 30 min (± 3 min)

Post-infusion: At EOI (±5 min), 1 hr (±5 min) and 2 hr (±10 min), 4 hrs (±10 min) following EOI. On Cycle 1 Day 1 additional timepoints include 6 hrs (±10 min) and 8 hrs (±10 min) following EOI.

Additional vital signs will be collected at the discretion of the investigator.

³ Full physical examination to be performed at Screening (including height), Day 1 Predose, and End of Treatment; all other physical examinations may be symptom directed. Weight to be collected on Day 1.

⁴ ECGs to be performed after the patient has been supine for at least 10 minutes. Readings should be performed with the patient in the same physical position. ECG recording should be taken in triplicate with 5-10 minutes between readings.

⁵ PK timepoints are as follows:

- Cycle 1 Day 1: ALRN-6924 samples: within 1 hour before SOI; at EOI (+5 min) and at 30 min (±5 min), 1-hour (±5 min), 2 (±10 min), and 4 (±10 min) hours after EOI.
- Cycle 1 Day 2: ALRN-6924 sample: 24 hours (±2 hours) post EOI; palbociclib: 18 hours (±2 hours) post dose
- Cycle 1 Day 8 and 15: ALRN-6924 samples: within 1 hour before SOI; at EOI (+5 min), Palbociclib samples: within 1 hour before SOI; at EOI (+5 min) of ALRN-6924 dosing.
- Cycle 1 Day 22: palbociclib: any time on Day 22

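### AE and SAE reporting starts at first dose, so a serious complication of a pre-dose study biopsy need not be reported to the sponsor, even in a patient who is never dosed

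*Protocol*

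**What the plan says.** **Reporting window (Protocol).**
- Section 8.2: "The AE reporting period begins from the date of the first study drug administration". It refers to Section 8.4 for SAEs.
- Section 8.4 sets the duty to report within 24 hours for "Any SAE, regardless of relationship to study treatment that occurs during therapy or within 30 days after the last dose of study treatment". After that, only related SAEs are reportable.
- Section 8.5 on follow-up: "For SAEs occurring from the patient's first administration of study treatment".
- Appendix C, for DR-A and DR-A-2: "AE reporting begins at the point of the first ALRN-6924 infusion". The schedules for DR-B and DR-C carry the same footnote.
- Appendix I, for the palbociclib combination: "AE collection period begins with first dose of ALRN-6924 until 30 days post last dose or start of subsequent therapy".

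**AE definition.** Section 8.1.1 is wider. It covers changes "occurring in any phase of the clinical study whether or not temporally associated with the administration of study medication".

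**Biopsies before dosing.** Section 6.3 requires a pre-dose sample, fresh or archival, to go to the central laboratory for molecular testing. For the dose escalation and PTCL cohorts, Section 3.2 bars enrollment of a patient who has no archived tissue and for whom biopsy carries significant risk. Without archived tissue, a fresh biopsy is thus the only way in. For the PTCL cohorts, Section 3.2.1 adds that "optional biopsies will be taken for PD and p53 status determination purposes: one during screening". Section 6.2 places all study-specific procedures after consent, which may be a separate molecular screening consent.

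**The concern.** A biopsy done to qualify a patient for this study is a study procedure, and its complications are harms caused by the study. The reporting rules are built around the drug and begin with it, so they do not reach a harm that occurs between consent and Day 1. Two things are at stake. The sponsor and the Safety Review Committee have no required route by which to learn of a serious bleed or similar event from a screening biopsy. And in a patient who then never receives drug, the event has no place in the safety data at all.

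**Working it through.** No formula applies and the plan gives no figure to reproduce. The check sets every clause that fixes the start of reporting against every clause that places a biopsy before dosing, and then follows one event through the rules.

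**1. Is there any pre-dose window?** Sections 8.2, 8.4 and 8.5 and the schedules for all regimens (Appendices C to I) start at first administration or during therapy. Section 8.2's reference to 8.4 does not rescue SAEs, because the 8.4 window also opens with therapy. No clause sets a window from consent to first dose or a rule for procedure-related events.

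**2. How likely is a fresh biopsy?** It is not universal, because archived tissue is allowed. But archived tissue is restricted:
- Dose escalation and PTCL: no more than one year old (Section 3.2).
- PTCL: the synopsis also rules it out after intervening systemic cytotoxic therapy, in patients with one to seven prior regimens (Section 4.3).
- Combination cohort: it must post-date any CDK4/6 inhibitor exposure (Section 4.5).
- Dose escalation after a prior MDM2 inhibitor: the biopsy must follow that treatment (Section 4.2).

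Footnote 1 of Appendix C itself speaks of a study biopsy taken shortly before enrollment, so the protocol regards these as study procedures.

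**3. How long is the uncovered interval?** The synopsis puts central testing at about two weeks, and Section 5.3 allows 21 days from the start of clinical screening to treatment. When the result is awaited, a biopsy can precede the reporting period by two weeks or more.

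**4. What happens to the event if the patient is dosed?** It meets the 8.1.1 definition but predates the 8.2 period. If it is still present on Day 1 and does not worsen, 8.1.1 treats it as a pre-existing condition. If a site volunteers it, Section 8.3.2 offers causality to study treatment only, and *Unrelated* expressly includes events that come too early.

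**5. What happens if the patient is not dosed?** Section 4.8 foresees patients who finish screening without a dose and replaces them. From escalation Dose Level 4, wild-type TP53 is mandatory, so the biopsy result itself can cause the screen failure. Protocol Section 7.3 limits the safety population to dosed patients. For Phase 1, SAP 3.2.2 counts a patient as enrolled only once dosed, SAP 5.1 limits the Safety Population in the same way, and SAP 8.3 counts treatment-emergent events from first dose. The event appears in none of these.

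**6. How many events?** The documents give no number of fresh biopsies, no complication rate and no number of screen failures. Planned enrollment of about 180 does not help, since it leaves out patients who are biopsied but never dosed.

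**The case against.** A reader might infer that these events go wholly unreported and are invisible to the sponsor. The documents do not support that:
- Section 10.2 obliges the investigator to keep the IRB informed of significant AEs, with no first-dose limit.
- Section 8.4 encourages discussing unclear reportability with the Medical Monitor, and Section 5.3 asks for the same where treatment is delayed.
- For dosed patients, medical history (Section 6.5, tabulated under SAP 7.2) and medications from 28 days before Day 1 (Section 6.11) can show traces of a complication.

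These routes stand as facts. None of them is a duty to report a pre-dose event to the sponsor, and those that run through the study database do little for a patient who is never dosed.

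A reader might also infer that the biopsy policy cannot be judged on safety at all. That goes too far. Optional on-treatment biopsies fall inside the reporting period. The synopsis forbids fresh biopsies of significant risk and requires the lowest-risk site and procedure. These safeguards lower the risk but do not reveal a complication when one occurs.

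It is also fair to say that a collection window narrower than the AE definition is not in itself a contradiction, and that treating an unresolved pre-dose event as baseline is right for attributing drug effects. Both points are accepted. The case rests on the missing reporting duty, not on a conflict between 8.1.1 and 8.2 or on the analysis sets. Finally, the Laboratory Manual holds biopsy details that are not available here. It could contain instructions, but Section 8 does not point to it for safety reporting.

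**Conclusion.** The gap is real and narrow. A serious complication of a biopsy done for the study before first dose is not required to be reported to the sponsor, and in a patient who is never dosed no safety dataset or analysis set captures it. On-treatment biopsies are not affected.

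Its size in events cannot be derived from the documents. Any count would need an assumed share of patients with fresh biopsies and an assumed complication rate, and the documents anchor neither. Few events would be expected if the biopsy safeguards are followed. No DLT, MTD or response analysis changes, and no drug-safety table is wrong. This is a low-cost improvement in the monitoring of harms caused by study procedures. It rests on reading the protocol text alone and assumes that no unseen manual already imposes the duty.

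**What to change.** Amend Sections 8.2 and 8.4, align Section 8.5, and update the AE footnotes in Appendices C to H and the AE row in Appendix I, along these lines:

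*From signature of the first consent (molecular screening or main study) until first dose, SAEs and AEs related to a protocol-required or optional study procedure are reported to the sponsor on the Section 8.4 timelines, including in patients who are never dosed. Relationship to the procedure is recorded. From first dose, the existing rules apply.*

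Add a causality item for study procedures beside the study-treatment scale in Section 8.3.2. Add one separate listing of these events, covering patients never dosed, to the Phase 1 SAP and to the separate Phase 2a plan. Leave the Safety Population and treatment-emergent definitions unchanged.

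Keep the pre-dose duty to procedure-related events. Collecting SAEs of any cause from molecular screening consent would bring in disease-related events in patients with advanced cancer and would go beyond the gap.

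Cost: amendment wording, slightly more site reporting before dosing, a way to record events in patients not dosed, and one extra listing.

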8.3. ADVERSE EVENTS

Treatment-emergent adverse events (TEAEs) are defined as AEs that are newly occurring or worsening on or after the date of the first dose of ALRN-6924. Reported AE terms will be coded using MedDRA version 19.1 or later.

The number and percent of subjects, and the number of events where relevant, will be summarized by SOC and PT for the following categories of TEAEs:

- All TEAEs
- Grade 3 or higher CTCAE grade TEAEs
- Related TEAEs defined as at least possibly related, as delineated by the investigator, or missing
- Serious TEAEs

- Serious related TEAEs
- TEAEs leading to discontinuation of study drug
- TEAEs leading to death

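### The SAP gives treatment-emergent AEs no end date and the protocol's end rules for AE and SAE reporting conflict, so late events can enter the Phase 1 ALRN-6924 safety tables

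*Protocol*

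**What the plan says.** The protocol states the end of AE reporting in several places, and they do not agree.

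- **Section 8.2** opens the period at first dose and says that it "ends 30 days after the last dose of study drug or a subsequent anticancer therapy is started, whichever occurs first". It refers to Section 8.4 for SAE reporting and to Section 8.5 for follow-up.
- **Appendices C to H** (the schedules for DR-A, DR-A-2, DR-B and DR-C) carry a common footnote: "AE reporting begins at the point of the first ALRN-6924 infusion until 30 days after last infusion or start of subsequent therapy". It goes on "until all drug-related toxicities and ongoing SAEs have resolved, whichever is later", with a further alternative that the investigator judges the AE chronic or stable.
- **Appendix I** (palbociclib combination, Cycle 1) says "AE collection period begins with first dose of ALRN-6924 until 30 days post last dose or start of subsequent therapy". It does not say whether the earlier or the later of the two dates applies, and it has no clause on resolution.
- **Section 8.4** requires any SAE "that occurs during therapy or within 30 days after the last dose of study treatment must be reported", with no cut-off at new therapy. After day 30 it requires related SAEs only, with no end date. Every SAE is also entered on the AE page of the eCRF.
- **Section 8.5** says that AEs and SAEs "within 30 days after the last administration of study treatment or withdrawal from the study must be reported unless the patient starts new anticancer therapy". Related events "should be followed until resolution or stabilization, or until the patient starts new therapy".

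SAP 8.3 defines TEAEs as "AEs that are newly occurring or worsening on or after the date of the first dose of ALRN-6924". The partial-date rules in SAP 3.3 also test an AE only against the date of first dose. By its Section 3.1, this SAP covers the Phase 1 dose escalation only.

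**The concern.** Safety and tolerability is a primary objective of Phase 1, and the TEAE tables are its main output. A treatment-emergent definition should state which events may be attributed to the period of exposure. This one has a start but no end, so the window is set by whatever the sites record, and the protocol gives the sites conflicting rules on when to stop.

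Two kinds of event are at stake. One is an event that starts or worsens after the patient has moved to another anticancer drug. The other is a related SAE long after the last dose, which should be reported but belongs to a different observation period from the rest of the table. Under SAP 8.3 both are counted as ALRN-6924 TEAEs, with nothing to mark them.

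**Working it through.** No power, alpha or event count is involved, and the plan states no figure to reproduce. The check is date logic.

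**Notation.** Count days from the last dose (day 0). T is the start of new anticancer therapy, and R is the day when drug-related toxicities and ongoing SAEs have resolved.

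**Rules as written**

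- Section 8.2: end = min(30, T).
- Appendices C to H: end = max(30 or T, R), unless the AE is judged chronic or stable. The choice between 30 and T is not stated.
- Appendix I: end = 30 or T, choice not stated.
- Section 8.4: all SAEs to day 30; after that, related SAEs with no end.
- Section 8.5: new AEs and SAEs to day 30 (or 30 days from withdrawal), stopped by T.
- SAP 8.3 and 3.3: every recorded event from first dose, no end.

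**Three cases with assumed dates**

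| Rule | Case 1: T = 10, R = 50 | Case 2: no new therapy, R = 50 | Case 3: no new therapy, nothing ongoing |
|---|---|---|---|
| Section 8.2 | min(30, 10) = 10 | 30 | 30 |
| Appendices C to H, read literally | max(10 or 30, 50) = 50 | max(30, 50) = 50 | 30 |
| Appendix I | 10 or 30 | 30 | 30 |
| Section 8.4, all SAEs | 30 | 30 | 30 |
| Section 8.4, related SAEs | no end | no end | no end |
| Section 8.5, new events | 10 | 30 | 30 |
| SAP TEAE | no end | no end | no end |

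**Reading the cases**

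1. Take Case 1 with an SAE on day 20, ten days into the new drug. Sections 8.2 and 8.5 have closed, but Section 8.4 requires the report and puts it on the AE page. SAP 8.3 makes it a serious TEAE.
2. Take Case 1 with a non-serious AE on day 20. It lies outside Sections 8.2 and 8.5 but inside the literal footnote. If the site records it, SAP 8.3 counts it.
3. In any case, a related SAE on day 60 is required by Section 8.4 and is counted as a TEAE.
4. In Case 3 with no late related SAE, the protocol rules agree on day 30.

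The rules therefore diverge only for patients who start new therapy before day 30, have a toxicity or SAE unresolved at the Section 8.2 end date, or have a late related SAE. The route through Section 8.4 does not depend on how the footnote is read.

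**What one patient can do to a table.** SAP 3.1 tabulates by dose cohort. Protocol Sections 5.5.3 and 5.7.1 give cohorts of 3 to 6 patients, and up to 6 more if the SRC adds them. If a late event is a patient's only occurrence of that term, it moves the cohort incidence by 1/3 = 33 points, 1/6 = 17 points or 1/12 = 8 points. This is the effect of one such patient; it does not estimate how many there are.

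**The case against.** The strongest reply is that the footnote concerns follow-up and opens no second collection window. Section 8.5 separates reporting of new events from follow-up of related ones. The footnote speaks of ongoing SAEs and of AEs judged chronic or stable, terms that fit events already recorded. Section 6.13 makes the visit about 30 days after last dose the end of study in Phase 1, and the long-term contact in Appendices D and F is for EXP only, so no later Phase 1 visit exists to collect new non-serious AEs. This is a plausible account of the intent, and it makes the leak uncertain for non-serious AEs. It does not remove it: the footnote says reporting, the SAP counts worsening as well as onset, and the Section 8.4 route for SAEs is unaffected.

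A reader might also infer three stronger things that the documents do not support.

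- **That the schedules choose the later of 30 days and new therapy.** They do not. The later date is set against resolution of toxicities and ongoing SAEs, and Appendix I has no such clause.
- **That patients with unresolved toxicity have inflated AE incidence, so cohorts cannot be compared.** The Phase 1 schedules (Appendices C to F) all carry the same footnote, so the wording makes no difference between Phase 1 regimens. DR-C and the combination lie outside this SAP. Longer observation of new events is possible but not shown.
- **That the effect can be given as a percentage of observation time.** For example, 60 days on treatment plus 30 makes 90, and 30 more makes 120, or 33% longer. Those durations are assumed, and calendar time for one hypothetical patient is not AE incidence.

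**Conclusion.** As written, the plan is wrong on this point. The protocol's end rules conflict, and the SAP's TEAE definition, with its partial-date rules, applies none of them. In the Phase 1 tables, an SAE recorded after new therapy or a related SAE recorded after day 30 counts as an ALRN-6924 TEAE under the stated rule. A non-serious AE recorded late would be counted in the same way, but how often that would happen depends on how sites read the footnote.

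The effect is confined to the patients described above. Its size cannot be computed, because the documents give no number of such patients or events. DLT-based escalation rests on Cycle 1 and is not affected, and the safety analysis is descriptive, so no test or error rate is at risk. The SAP is based on protocol Amendment 6 and the protocol reviewed is later, but the missing end date is in the SAP's own text and does not come from that gap.

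**What to change.** 1. **SAP 8.3.** Define a TEAE as an AE with onset or worsening from first dose through the earlier of 30 days after last dose and start of new anticancer therapy, to match Section 8.2. Extend the partial-date rules in SAP 3.3 to this end date.
2. **Separate listing.** List all SAEs reported outside that window: those between new therapy and day 30, and later related SAEs. They should not be added back into the TEAE definition, because that would restore the open-ended window; and they should not be dropped, because Section 8.4 requires them to be reported.
3. **Protocol.** Reconcile Sections 8.2, 8.4 and 8.5, in particular whether new therapy ends SAE reporting before day 30. Reword the footnotes in Appendices C to H so that the later date applies only to follow-up of events already reported. State in Appendix I which of its two dates governs.

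The cost is one definition and one listing in the SAP, and wording edits in the protocol. No new assessments are needed. The sponsor should confirm that the start date of new therapy is on the Phase 1 eCRF: Section 8.2 already relies on it, but the scheduled long-term collection of subsequent therapies is for EXP only. The separate Phase 2a plan should use the same definition.
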